## B. Study Design and Research Methods

Participants will complete two study visits and one online assessment, with procedures listed in this table and described below.

### Assessment, Visit 1, Day 1

This visit will occur at the Pediatric Mental Health Institute (PMHI) outpatient clinic in a private laboratory room (see COMIRB Application, Section Q, for facilities description).

Adolescents and their parent will begin with a session to obtain informed consent and assent with study personnel (see COMIRB Application, Section L, for procedure). Clinical assessment will begin with the parent and adolescent will each complete their respective versions of the Affective Reactivity Index (ARI) to

Clinical Assessment	Training	Post training Assessment
Day 1	Up to Day 7	1 week ± 3 days after training
Clinic	Clinic	Online
Consent	IBT	ARI
ARI		Scales
WASI		
KSADS		
C-SSR		
Scales		

measure level of irritability. Adolescents with mild clinical irritability will be invited to continue (parent-report ARI  $\geq$  3 or self-report ARI  $\geq$  2; based on sensitivity analyses in Kircanski et al.).

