For those randomized to out-of-scanner conditions, this visit will occur at the Anschutz Medical Campus Gary Pavilion outpatient psychiatric clinic in a private laboratory room. For those randomized for in-scanner conditions, this visit will occur at the Anschutz Medical Campus Brain Imaging Center (BIC). See COMIRB Application, Section Q, for facilities description. See COMIRB Application, Section J, for MRI safety screening procedures.

At the start of the second visit, adolescents will complete an out-of-scanner interpretation bias assessment on a laptop approximately 3 minutes. Adolescents will then complete an in- or out-of-scanner session of active or sham IBT depending on their allocation (approximately 18 minutes). Immediately after IBT, all adolescents will complete an out-of-scanner interpretation bias assessment presented on a laptop. To assess whether training on the ‘prototypical’ male face-set generalizes to other face-sets, adolescents will complete another interpretation bias assessment designed by [name] and colleagues. It has nearly identical trial structure, but uses four NimStim^63 face-identities that differ in gender and race along the same 15-morph continuum and takes 7.5 minutes to complete. Details of these cognitive tasks and image acquisition are provided below.

At the end of this session, we will give participants a RedCap link and log on instructions. We will ask them to complete an online assessment via RedCap in one week. For those who opt against completing their assessment online, we will give them a packet of assessment measures.

Based on pilot experience at the NIMH, I anticipate the visit length for each out-of-scanner arm to be one hour long and the visit length for each in-scanner arm to be two hours.

*While COVID-19 safety procedures are still in effect on the Anschutz Medical Campus, the following adaptations will be made to Training, Visit 2, Up to Day 7:*

Adolescents and their caregivers will be screened for COVID-19 symptoms the day before their scheduled Visit 2 in accordance with CHCO site standards or BIC standards, depending on randomization.

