#### Assessment, Online, About one Week after IBT

The day before it is due, Drs. [name] or [name] will call the family to remind them to complete their follow up assessment. Drs. [name] or [name] will ask parents, “Do you have new concerns about your child since the training session?” The scales included in this assessment are the same as in the first visit, excluding the Tanner Scale. In addition, during the post-training assessment, adolescents will complete the Intent Attributions

Questionnaire, another measure of interpretive bias (10 minutes). Because this scale can only be administered every six months, we are limited to a post-training assessment only. Though we cannot assess IBT-associated changes in ratings on this scale, we can assess for both associations with irritability as well as differences in hostile attribution bias between those in the sham vs. active IBT groups.

For online assessments, adolescents will complete the following self-report forms:

1. Short Moods and Feelings Questionnaire (MFQ; 2 minutes)
2. Screen for Childhood Anxiety Related Emotional Disorders (SCARED; 8-10 minutes minutes)
3. Affective Reactivity Index (ARI; 2 minutes)
4. State-Trait Anger Expression Inventory-2 Child and Adolescent (STAXI-2 C/A; 5-8 minutes)
5. Intent Attributions Scale (10 minutes)

During this visit, caregivers will complete the following parent-report forms:

1. ARI (2 minutes)
2. SCARED (8-10 minutes)
3. MFQ (2 minutes)
4. SNAP-IV, items 1-40 only, (5-10 minutes)

Based on conducting similar online assessments at the NIMH, I anticipate this assessment to take approximately ½ hour for the adolescent and 15 minutes for their caregiver.

*Interpretation Bias Training Session.* The interpretation bias training session consists of an assessment of interpretation bias followed by trainings to shift the bias. A training session is depicted in Figure 1.

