Hypothesis 1.2: Active but not sham, IBT will reduce hostile interpretation bias. Mixed-effects linear regression with balance point (interpretation bias) as a dependent variable and training condition (active vs. sham), and time of interpretation bias assessment (pre- or post-training) as independent variables of interest and person as a grouping variable and random effect. Similar models will test for group differences in active or sham IBT on other measures of hostile interpretation bias after training.

Hypothesis 2.1: The rate of learning new associations to ambiguous faces training will be associated with baseline irritability. For those in the active condition, linear regression will test the association between pre-training ARI (irritability) and learning rate to reversal feedback of baseline angry judgments to the two ambiguous morphs.

Hypotheses 2.2 and 2.3: Active, but not sham, IBT will evoke greater neural response in threat-learning systems. For each person, learning will be modeled with regressors coding the “value” or trialwise likelihood that a participant considers the morph to be angry. The amplitude of BOLD %signal change (activity) or amygdala covariance (generalized psychophysiological interaction; connectivity) related to these regressors represents neural response to value. Critically, these regressors represent learning itself where value is changing towards benign judgments in the active training condition to two ambiguous morphs. These will be carried forward to the second level mixed-effects linear models of the effects of morph by pre-training ARI by training condition. A voxel-wise threshold of  $p < .001$ , whole-brain, cluster corrected to  $p < .05$  via permutation testing or Monte Carlo simulation as appropriate, will be used to identify significant associations. A three-way interaction of change in value by morph by training condition will indicate neural areas where learning is influenced by irritability in active but not sham training of reversals of ambiguous morphs. In addition, our *a priori* identification of the likely role of the amygdala, OFC, and ACC justifies follow-up region-of-interest analyses of mean activity or connectivity extracted from these areas with the same omnibus mixed-effects model.

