Exploratory Hypothesis 3.1: Change in irritability after training is associated with change in hostile interpretation bias. We will investigate this relationship with mixed-effects linear models with ARI (irritability), balance-point (interpretation bias), and time of assessment (pre- or post-training) as within-person variables.

Exploratory Hypothesis 3.2: Change in irritability after training is associated with magnitude of neural threat-learning system response. We will investigate this relationship with mixed-effects linear models with ARI (irritability), mean value-associated connectivity or activity in the amygdala, OFC, and ACC, and time of assessment (pre- or post-training) as within-person variables.

As requested by NIMH scientific review, I will conduct two additional, secondary analyses: 1) a mediation analysis of active IBT on change in irritability and 2) a multivariate analysis of the shared and unique effects of irritability, anxiety, and depression on hostile interpretation bias.

Power analysis. For Aim 1, a sample size of 100 achieves 80% power to detect an effect size of the expected association of at least  $r = .25$  between baseline hostile interpretation bias and baseline irritability using Pearson correlation at a one-tailed alpha of .05. Thus, the proposed study will have sufficient power to detect small to medium sized interaction effects. The study is overpowered for detecting expected effects of IBT on hostile interpretation bias which should be large. For Aim 2, a sample size of 100 likewise achieves more than 80% power to detect the expected large association between baseline irritability and learning. For imaging, using a medium effect size of a term in a general linear model ( $R^2 = .15$ ), the required sample for 80% power is 50 individuals ( $p = .05$ ). Our previous study that examined IBT-related changes to face-emotions was medium to large in the orbitofrontal cortex. Thus, the proposed study will have sufficient power to detect small to medium sized interaction effects. Aim 3 is exploratory; this study may estimate effect sizes for future research.

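### Exploratory Hypothesis 3.2 treats the neural measure as varying from pre- to post-training, but task fMRI is acquired in one session only; Hypothesis 3.1 should also name its outcome and tested term

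*Combined protocol and SAP*

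**What the plan says.** Section F (Data Analysis Plan) states Exploratory Hypothesis 3.2 as "Change in irritability after training is associated with magnitude of neural threat-learning system response". Its model is a mixed-effects linear model with ARI, "mean value-associated connectivity or activity in the amygdala, OFC, and ACC, and time of assessment (pre- or post-training) as within-person variables". Hypothesis 3.1, on change in irritability and change in hostile interpretation bias, is to use "mixed-effects linear models with ARI (irritability), balance-point (interpretation bias), and time of assessment (pre- or post-training) as within-person variables". Neither sentence names a dependent variable, a tested coefficient or a training-condition term.

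On data collection, section B (Study Design and Research Methods) says "Participants will complete two study visits and one online assessment, with procedures listed in this table and described below". Under Training, Visit 2, participants first do a bias assessment outside the scanner. Then "Adolescents will then complete an in- or out-of-scanner session of active or sham IBT depending on their allocation", and "Immediately after IBT, all adolescents will complete an out-of-scanner interpretation bias assessment presented on a laptop". Of the one-week online follow-up the protocol says "The scales included in this assessment are the same as in the first visit, excluding the Tanner Scale".

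Section I (Specific Aims) limits Aim 3 to change in irritability following active training. Its wording can be read as relating this to change in threat-system response. The power paragraph calls Aim 3 exploratory and says only that it may yield effect sizes for later research.

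**The concern.** A variable measured once per person has no within-person change from pre to post. The Hypothesis 3.2 model sentence therefore describes a data structure that the schedule does not produce, and an analyst must replace it with something the plan does not state. Which term is then tested matters. The neural main effect asks whether neural response relates to the overall level of ARI. Only neural-by-time asks whether it relates to change in ARI.

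Hypothesis 3.1 has a milder form of the same gap. Balance point is measured twice, so its model can be fitted. However, an uncentred time-varying predictor in a random-intercept model blends the within-person association with the between-person association, and Hypothesis 1.1 expects the latter to be non-zero. At stake is whether a baseline association could be reported as change tracking change and carried into the planning of an efficacy trial.

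**Working it through.** The plan gives no sample size, power or error rate for Aim 3, so there is no stated figure to reproduce.

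**Step 1. When each Hypothesis 3.2 variable is measured.**

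| Variable | Before training | During training | After training |
|---|---|---|---|
| ARI | Visit 1 | – | Online, 1 week ± 3 days |
| Balance point | Visit 2, laptop | – | Visit 2, laptop |
| Task fMRI | none | Visit 2, scanned arms | none |

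Pre/post neural pairs per person: 0. The six training blocks and the several morphs give more than one neural value per person, but all come from the training session. The plan specifies a mean measure and a pre- or post-training time factor. The Hypotheses 2.2/2.3 text plans "follow-up region-of-interest analyses of mean activity or connectivity extracted from these areas with the same omnibus mixed-effects model", which also draws on that one session.

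**Step 2. What can be fitted.** Let M be one neural value per person. In a balanced two-occasion random-intercept model of ARI:
- the M main effect (model without interaction) equals the regression of person-mean ARI on M;
- the M × time coefficient equals the regression of ARI change on M.

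Only the second is Hypothesis 3.2. Suppose M correlates .25 with stable irritability, ARI has intraclass correlation (ICC) .7, and nothing predicts ARI change (all assumed). The correlation of M with mean ARI is .25 × √(.7/.85) = .227. With Fisher z, atanh(.227) × √(n−3) = .231 × 6.856 = 1.58 at n=50 and .231 × 4.690 = 1.08 at n=25. The main effect would then reject at two-sided .05 in about 35% and 19% of trials. Simulation gave 36% and 19%, and about 5% for M × time.

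**Step 3. Hypothesis 3.1, only if the uncentred balance-point coefficient is tested.** Use unit variances, baseline correlation r, ICCs a (ARI) and b (balance point), and no true link between changes. The coefficient is a weighted mean of the within-person slope (0) and the between-person slope 2r/(1+b). The weights are (1−b) and λ(1+b), where λ is the within-person residual variance over the between-person residual variance (twice that of the person mean).

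Example with a = b = .7 (assumed) and r = .25 (the plan's expected value for Hypothesis 1.1):
- between-person slope = .50/1.70 = .294
- λ = .307/1.586 = .194
- weights .300 and .194 × 1.70 = .329
- expected coefficient = .329/.629 × .294 = .154, when the true change slope is 0
- standard error at n=50 = √(.307/(50 × .629)) = .099, so z = 1.56 and rejection is about 34% (simulation: 36%)

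The same steps at r = .10 give a coefficient of .059, z = .59 and rejection of about 9%.

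Simulation covered ICCs of .6 to .9 for ARI and .5 to .7 for balance point, with balance-point shifts independent of, or dependent on, the person's own level. At n=50 the uncentred term rejected in roughly 10-40% at r = .25 and about 6-14% at r = .10. Change-on-change rejected in 4-6%.

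**Step 4. Limits of change scores.** If both shifts depend strongly on the person's own level (coefficient .6), change-on-change rejects in 8-14% (n=50, r=.25), against 5-7% for baseline-adjusted ARI. If only the balance-point shift does, baseline-adjusted ARI rejects in 6-9%. Neither is safe everywhere.

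**Step 5. Precision.** The half-width around r = 0 is tanh(1.96/√(n−3)): .278 at n=50 (active arm, Hypothesis 3.1) and .395 at n=25 (scanned active arm, Hypothesis 3.2). These n are accrual targets for acceptable task and scan data, not for completed one-week ARI. If a fifth lacked follow-up (assumption), the half-widths would be .312 (n=40) and .443 (n=20).

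**The case against.** The strongest reply is that Hypothesis 3.2 contains a labelling slip. Its hypothesis sentence asks about magnitude, which one scan supplies. ARI is measured before and after, and the text nowhere says that scanning is done twice. This stands in part. A reader might infer that the trial lacks the data for Hypothesis 3.2, and the documents do not support that. The model sentence still assigns the neural term a role it cannot have and leaves the correct term unstated.

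For Hypothesis 3.1, a reader might infer that the plan commits to a test with an inflated false-positive rate. It does not. The hypothesis is change with change, and balance point is called a within-person variable. Both favour the within-person reading, for which rejection is about 5%. The 10-40% range needs the other reading and assumed ICCs. It also takes r = .25, which the Background section derives from a contrast of DMDD with youths without psychopathology, whereas this sample has an ARI entry threshold.

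A reader might also infer that training arm is ignored. The Specific Aims limit Aim 3 to active training, section F promises omnibus models throughout, and a mediation analysis of active training follows Hypothesis 3.2. What remains is that the two model sentences do not say how condition enters.

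Finally, Aim 3 is exploratory with no power claim. That limits the weight of the point, but it does not supply a second neural measurement.

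**Conclusion.** The Hypothesis 3.2 model is wrong as written. This rests on the documents alone: one task-fMRI session, no pre/post neural pair, and a model sentence that requires one. The hypothesis can still be tested with the scheduled data once the neural measure is treated as between-person.

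The Hypothesis 3.1 point is secondary and conditional. The outcome and tested term are unnamed, and the numerical consequence arises only under an uncentred test and the stated assumptions. It is small if the baseline association is weak.

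The point deserves correction because it costs only wording and Aim 3 is meant to inform a later trial. It does not affect Aims 1 or 2. It also does not imply that corrected analyses will in general give fewer significant results. That would follow only if the uncentred term would otherwise have been tested and a baseline association exists.

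**What to change.** **Hypothesis 3.2.** Make ARI (Visit 1 and one week) the outcome. Enter the single-session neural estimate as a between-person predictor and delete the within-person label for it. Test neural × time (equivalently, ARI change on the neural estimate), with training condition and its interaction. Report the active-arm slope with its 95% CI. Define the neural summary so that it exists in both arms, because sham training reinforces the current balance point and retrains no morphs. One option is the response to the two ambiguous morphs nearest the balance point that were rated angry before training: retrained in the active arm, position-matched in sham. Otherwise limit the analysis to the active arm. Align the Aim 3 wording in the Specific Aims with the magnitude wording in section F.

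**Hypothesis 3.1.** State that the within-person association is tested: ARI change (one week minus Visit 1) on balance-point change (Visit 2 post minus pre), with condition and its interaction. A person-mean-centred balance-point term in the mixed model is the same test with two occasions, so it is not an extra safeguard. Give baseline-adjusted ARI as a sensitivity analysis.

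**Cost.** Plan wording only, with no new data or visits. The price is candour about precision: the intervals in Step 5 are wide, and wider still if follow-up ARI is incomplete.

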### **I. Hypotheses and Specific Aims:**

Chronic irritability is a prominent dimension of pediatric psychopathology for which evidence-based treatments are scarce, have limited efficacy, or adverse side effects. There is a need to develop novel treatments, especially those that target the neurocognitive basis of irritability. One candidate is Interpretation Bias Training (IBT), a computer-based training designed to target rapid, automatic processing of social information. In a small open trial, IBT showed promise as an acceptable, feasible treatment for irritability. However, its underlying neurocognitive targets have not been established. In order to translate IBT for clinical use, we propose to examine two promising neurocognitive targets of IBT.

**Specific Aim 1:** Establish hostile interpretation bias as a treatment target for irritability and engage it through interpretation bias training. One hundred adolescents, drawn from an outpatient psychiatric clinic with varying degrees of clinically significant irritability, will be randomized to a session of active (n=50) or sham (n=50) IBT.

Hypothesis 1.1: The degree of hostile interpretation bias is positively associated with clinical irritability

Hypothesis 1.2: Active but not sham interpretation bias training will reduce hostile interpretation bias.

**Specific Aim 2:** Establish the ability to learn benign judgments of ambiguously hostile social information as a treatment target for irritability and engage it through interpretation bias training. A subsample of 50 participants (n=25 in each active and sham group) will train during fMRI.

Hypothesis 2.1: Learning rates during active IBT will be associated with baseline irritability.

Hypotheses 2.2, 2.3: In neural systems underlying threat learning, response while learning new associations during active IBT will be related to clinical irritability in terms of both neural activity (2.2) and functional connectivity (2.3).

[figure not shown]
**Exploratory Aim 3:** Provide preliminary evidence that changes in treatment targets are related to changes in irritability. To better establish the mechanism of target engagement and gather preliminary evidence for an efficacy trial, we will measure any changes in irritability after IBT. Therefore, we hypothesize that changes in irritability following active IBT will be associated with changes in hostile interpretation bias (hypothesis 3.1) and threat system response (hypothesis 3.2).

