#### Randomization

Within 48 hours of Visit 1, Drs. [name] or [name] will determine if any exclusion criteria are met. This time allows Drs. [name] and [name] to consult each other or clarify information with the participants to achieve consensus for any unclear exclusionary diagnosis. If so, [name] will call the participants to thank for their participation, inform them of their exclusion, and cancel their second visit. Some exclusionary criteria are not stable, and it is likely the participants will be eligible during the study period. In that case, participants will still be

marked as a “Screen Failure,” in the consented, but not enrolled, category. However, they will be offered the opportunity to reschedule in the future. In this case, the participants will need to repeat visit 1.

During the pilot phase, eligible adolescents will not be randomized to a study arm, but will be invited to follow procedures for any arm. After pilot, eligible adolescents will be randomized for a 2 x 2 factorial, single blinded, randomized controlled trial, eligible adolescents will be assigned to one of four arms representing TRAINING (active or sham IBT) and SCANNING (in- or out-of-scanner IBT). First, scan ineligible patients will be assigned to out-of-scanner training. Second, randomization will use established minimization procedures (R packages randPack and/or randomizeR) to ensure the four arms are similar in terms of sex, age, socioeconomic status (SES), and IQ. The single blind is required so I may track adolescents with acceptable data. Acceptable behavioral data are at least 70% accuracy on extreme morphs (see [name] et al. for the development of this threshold) and, if applicable, scans of acceptable quality (see below). Allocation to any arm will end when the accrual goal of 25 adolescents with acceptable data have been reached for a total N=100. Since this is a small trial that is not intended to assess clinical efficacy, promoting power and ensuring balance across confounds outweigh the potential for allocation bias due to single-blinding or minimization procedures.

#### Training, Visit 2, Up to Day 7

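### The power paragraph gives H2.1 power for 100 participants although only the 50 active ones are analysed, and its Aim 2 interaction claim goes beyond the calculation before it

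*Combined protocol and SAP*

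**What the plan says.** The power analysis in section F makes three relevant statements.

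- **Aim 1.** 100 participants give 80% power for r=.25 between baseline bias and irritability, "using Pearson correlation at a one-tailed alpha of .05". The next sentence reads: "Thus, the proposed study will have sufficient power to detect small to medium sized interaction effects".
- **Aim 2, learning (H2.1).** "For Aim 2, a sample size of 100 likewise achieves more than 80% power to detect the expected large association". No numeric value is given for large and no sidedness is stated; the word 'likewise' points back to Aim 1.
- **Aim 2, imaging.** The calculation is made "using a medium effect size of a term in a general linear model" (R²=.15), and at p=.05 "the required sample for 80% power is 50 individuals". The interaction sentence is then repeated word for word.

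The analysis itself is set out just above, in the same section. For H2.1: "For those in the active condition, linear regression will test the association between pre-training ARI (irritability) and learning rate". For H2.2 and H2.3 the second-level model crosses morph, pre-training ARI and training condition.

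On numbers, section I says that 100 adolescents "will be randomized to a session of active (n=50) or sham (n=50) IBT". It puts 25 of each group in the scanner. The Randomization section defines four arms and says: "Allocation to any arm will end when the accrual goal of 25 adolescents with acceptable data have been reached".

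**The concern.** The sample size in the H2.1 power statement is twice the number in the H2.1 regression. The full 100 cannot be meant as the analysed sample. The outcome is the learning rate to feedback that reverses angry judgments of two ambiguous morphs, and section B describes sham feedback as reinforcing the existing balance point instead.

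The interaction sentence begins with 'Thus', so it is offered as a consequence of what precedes it. Under Aim 1 that is a bivariate correlation. Under Aim 2 it is one unnamed model term whose medium size already uses the whole scanned sample.

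These are the plan's only statements of what H2.1 and the imaging interaction can detect. Section G says the project will supply the basis for a go/no-go efficacy trial, so a reader who weighs a null result needs the correct sensitivity.

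**Working it through.** **Inputs.** From the plan: r=.25, one-tailed .05, N=100 (Aim 1); R²=.15, p=.05, N=50 (imaging); four arms of 25 with acceptable data; pilot learning-rate contrast t(20)=1.88, d=0.84 (Figure 3 legend); d=0.51 equated with r=.25 (section II). Assumed here: r=.50 as a conventional large correlation, and f²=.02 and .05 as illustrative small effects.

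**Formulas.** For a correlation, by Fisher z: power = Φ(atanh(r)·√(n−3) − z_α), and the smallest r with 80% power = tanh((z_α + 0.842)/√(n−3)), with z_α=1.645 one-tailed or 1.960 two-tailed. For one model term: noncentral F with f²=R²/(1−R²) and λ=f²·N.

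**1. Reproduce the plan's figures.**
- Aim 1: atanh(.25)·√97 − 1.645 = 2.516 − 1.645 = 0.871, power 80.8%. The stated 80% is reproduced (two-tailed it would be 71.1%).
- Imaging: r=√.15=.387 and atanh(.387)·√47 − 1.960 = 0.84, power 80.0%. The stated 50 is reproduced. Noncentral F gives 82.9% at N=50.

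**2. H2.1 at the analysed sample.** Active participants = 2 arms × 25 = 50. The 21% loss allowance in the population section is already outside this number.

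| | n=50, one- / two-tailed | n=100, one- / two-tailed |
|---|---|---|
| Smallest r with 80% power | .35 / .39 | .25 / .28 |
| Power at r=.50 | 98% / 96% | 100% / 100% |
| Power at r=.39 (pilot) | 88% / 80% | 99% / 98% |

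For example, at n=50: tanh(2.487/√47)=.348 and tanh(2.802/√47)=.387. The pilot value is r = 1.88/√(1.88²+20) = .388, with a 95% CI of −.04 to .70. It is only an approximation, because it converts a contrast of DMDD with healthy youths, not a correlation within irritable patients.

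**3. Aim 2 interaction sentence.** With N=50 and uncorrected two-sided .05, the 80% limit for one term is R² of about .14 (noncentral F) to .15 (Fisher z). Below that, power drops: f²=.05 gives 34% and f²=.02 gives 17%. These are single-term figures. The plan gives no inputs from which power for the three-way mixed-model interaction could be computed.

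**4. Aim 1 interaction sentence.** The Aim 1 interaction is time by training condition (H1.2). With two time points and balanced data, its test equals a two-sample t test on the change score. At 50 per arm the normal approximation gives (1.645+0.842)·√(2/50)=0.497 one-tailed and (1.960+0.842)·√(2/50)=0.560 two-tailed; noncentral t gives 0.50 and 0.57 SD of change. As a correlation, d=0.50 is 0.50/√(0.50²+4)=.24, close to the stated r=.25. A small effect, f²=.02, has 29% power at N=100 two-sided (41% one-sided).

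In SDs of a single assessment, the two-tailed limit is 0.566·√(2(1−ρ)): 0.57 if the pre-post correlation ρ is .5, and 0.36 if it is .8. The plan does not give ρ.

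**The case against.** The strongest reply has four parts.

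- **The H2.1 conclusion survives.** This stands. A reader might infer that H2.1 is underpowered; the documents do not support that. For a large association, power stays well above 80%, and at the pilot-derived value it is about 80% even two-tailed. One could also read 100 as the trial total that yields 50 active participants, but 'likewise' ties it to the Aim 1 calculation, where 100 is the analysed sample.
- **The Aim 1 interaction sentence has some support.** This also stands. A one-degree-of-freedom interaction has about the same limit as a correlation of equal partial R², and section II itself equates d=0.51 with r=.25. A reader might infer that the sentence is baseless in both places; under Aim 1 the fault is only that the term, scale and sidedness are unstated and that 'small' is not covered.
- **An interaction is also a term in a general linear model.** True, and the plan does not exclude that reading. But it does not name the term, and even if the term were the interaction, R²=.15 is the plan's own medium and already sits at the 80% limit. 'Small' does not follow.
- **Nothing ties a null result to a decision.** Correct. Section G sets no rule based on H2.1 or an interaction, and it also calls the project hypothesis-generating. How a null might be misread is illustration, not something the documents state.

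**Conclusion.** Wrong as written; minor to should-fix, because no sample size or analysis is affected.

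- **H2.1:** the stated N is double the analysed N. The 80% limit is r=.35 one-tailed or .39 two-tailed, not .25 or .28. This rests on 50 evaluable active participants. The population section also mentions low-irritability volunteers, three for each arm on one reading, without saying whether they enter H2.1. Six more would make n=56, with a limit of tanh(2.487/√53)=.33 or tanh(2.802/√53)=.37, so the conclusion is the same.
- **Aim 2 interactions:** the claim contradicts the calculation before it. Effects below the plan's medium have less than 80% power in a single-term test at uncorrected .05. A reader might go further and infer that the three-way interaction is shown to lack power; it is not shown either way, because nothing is calculated for it.
- **Aim 1 interactions:** defensible at about r=.25, or 0.50 SD of the change score one-tailed, but not for a conventionally small effect.

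The separate statement that the study is overpowered for a large training effect on bias is not disputed.

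**What to change.** Change the wording of the power paragraph only.

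- **H2.1:** replace the statement for 100 with: *H2.1 is tested in n=50 active participants, giving 80% power for r of at least .35 (one-tailed .05)*, or *.39 (two-tailed .05)*. State which sidedness applies and the numeric value meant by large. Say whether the low-irritability volunteers are included.
- **Aim 2:** delete the interaction sentence, or replace it with: *at N=50 a single term of R² about .14–.15 is detectable with 80% power at uncorrected .05; power for the three-way interaction was not calculated*.
- **Aim 1:** replace the interaction sentence with the limit it supports: *with 50 per arm the time-by-condition interaction has 80% power for 0.50 SD (one-tailed) or 0.57 SD (two-tailed) of the change score*.

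The cost is that the stated sensitivity looks less favourable. Sample size, models and conduct stay as they are.
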